11.4 Phone call follow-up

For any subjects who withdraw prior to study exit, there will be a phone call within 7(+3) days to follow up on the subject's health.

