10.2 Treatment Sequence

At Visit 1, eligible subjects will be enrolled and scheduled for Visits 2 and 3. Subjects will be dosed as per a fixed sequence at Visits 2 and 3.

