10.3.2 Emergency Unmasking

Emergency unmasking should only be performed when necessary to treat the subject. Most often, knowledge of the possible treatment assignments is sufficient to treat a clinical trial subject who presents with an emergency condition.

The investigator should make every effort to contact the Medical Monitor to discuss the subject's emergency and the need to unmask prior to unmasking any subject.

In situations in which the investigator has tried but is unable to reach the Medical Monitor, best judgement on the part of the investigator should be used, based on the nature and urgency of the clinical situation, and may proceed with unmasking without having successfully reached and discussed the situation with the Medical Monitor. Once a subject's treatment assignment has been unmasked, the Medical Monitor should be notified within 24 hours of the unmasking of the treatment, without revealing the treatment.

As this is a fixed sequence clinical trial, every attempt will be made to maintain the masking for the other subjects in the event of an unmasking must occur, an unmasking procedure will be developed.

The emergency unmasking should be performed by the designated site personnel. The investigator must also indicate in source documents and the Case Report Form (CRF) that the mask was broken and provide the date, time, and reason for breaking the mask.

Any AE or Serious Adverse Event (SAE) associated with breaking the mask must be recorded and reported as specified in the protocol. The investigator has the responsibility to contact the

Sponsor (PI) in the event of a drug-related, serious, unexpected AE, the ProPharma Group or designee will be provided with the treatment assignment for the subject for regulatory reporting.

If treatment assignment is unmasked, the treatment will be discontinued immediately, and the subject will be discontinued from the clinical trial.

The mask may be broken in the case of pregnancy should the subject desire this information.

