11.2 Visit 1: Screening (Day -21 to -8)

The following activities will be completed at Visit 1:

- Subjects will be asked to sign and date the Informed Consent Form.
- Demographic data, including date of birth, age, race and ethnicity, will be recorded.
- Medical/Medication and Ocular history will be completed for each subject.
- A urine pregnancy test will be performed (for all female subjects). Subjects with a positive result will be excluded.
- The subjects will be evaluated for study inclusion, exclusion and restriction criteria.
- Symptom Questionnaires (Ocular Discomfort Score, Ocular Itching Score) will be performed within 15 minutes prior to DEC entry and every 5 +2 minutes up to 45 minutes while in the chamber.
- An SVA and SLE will be performed pre and post-DEC.
- IOP will be performed prior to DEC entry and dilated funduscopy will be performed post-DEC.
- Saline will be administered in the clinic approximately 5 minutes prior to the DEC entry.
- DEC session (approximately 45 minutes).
- Adverse events and concomitant medications will be recorded before the subject leaves the site.
- After 7 ± 1 day of washout period, eligible subjects will come to Visit 2

11.3 Visits 2 (Day 1 + 2) and 3 (Day 8 + 2): Treatment/Dry Eye Chamber

Eligible subjects will return for 2 treatment visits. The treatment visits will occur following at least 7 days after visits 1 and 2. At Visit 2 the subjects will be randomized to receive one of the 2 treatment sequences as mentioned in [Section 10.2](#). At Visits 2 and 3, the following activities will be performed:

- Medical/medication and ocular history will be updated for each subject.
- A urine pregnancy test will be performed (for all female subjects). Subjects with a positive result will be excluded.
- The subjects will be evaluated for study inclusion, exclusion and restriction criteria.
- An SVA and SLE will be performed pre and post-DEC.
- Symptom questionnaires (Ocular Discomfort Score, Ocular Itching Score) will be performed within 15 minutes prior to study treatment administration and approximately every 5 minutes while in the chamber.
- Test product will be administered in the clinic approximately 5 minutes prior to the DEC entry.
- DEC session (approximately 45 minutes).
- Dilated funduscopy will be performed post-DEC after SVA and SLE at Visit 3.
- Adverse events and concomitants medications will be recorded before the subject leaves the site.
- Study exit (Visit 3).

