12.2.7 Adverse Event Query/Concomitant Medication Query

The staff will record all adverse events observed, queried, or spontaneously volunteered by the subjects. An adverse event query will be performed as scheduled as per Investigator's direction throughout the post-dose confinement period, prior to being released from confinement, and at each return visit for the study (if applicable). Subjects will be asked non-leading questions such

as “How do you feel now?”, “How have you felt since last asked?” or “Have you taken any medication since last asked?” If the presence of any symptom(s), adverse event(s), and/or concomitant medication is recorded, the clinical staff may advise the subjects to remain at the clinic site for safety reasons until the Investigator decides it is safe for the subjects to leave. If the subject decides to leave despite the Investigator's advice, he/she will be asked to sign a waiver.

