14.2 Safety Analysis

Safety analysis will include descriptive analysis and listings according to received treatment. Safety analysis will be performed on all subjects receiving at least one dose of study medication. Subject's safety data will be presented according to the treatment they actually received. The Safety population will be used for all analyses of safety endpoints as well as demographics and baseline characteristics.

Adverse events and SAE will be classified using standard Medical Dictionary for Regulatory Activities (MedDRA) terminology Version 23.1 and presented by the treatment group. Summary tables listing the type, date of onset, date and time of resolution, incidence, severity, outcome, action taken, and Investigator's opinion of relationship to the study product will be presented by treatment group for AEs reported after randomization.

Concomitant medication used during the study will be listed by treatment and subject.

14.3 Interim Analyses No interim analysis is planned at this point.

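### Section 14.2 tabulates AEs by product with no common post-dose window; under a single fixed sequence, and if washout AEs go to the preceding product, background AEs fall almost only on the first product

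*Combined protocol and SAP*

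**What the plan says.** **Table.** Under Section 14.2 the AE summary covers type, onset, severity, outcome and related items, and the Investigator's "opinion of relationship to the study product will be presented by treatment group for AEs reported after randomization". Safety data follow the treatment actually received. No post-dose window is given. Nothing states which product an AE belongs to when it starts between the two dosing visits.

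**AE queries.** Section 12.2.7 schedules them during the post-dose stay, "prior to being released from confinement, and at each return visit for the study (if applicable"). For Visits 2 and 3, Section 11.3 says: "Adverse events and concomitants medications will be recorded before the subject leaves the site". Study exit is at Visit 3. The follow-up call in Section 11.4 reads: "For any subjects who withdraw prior to study exit, there will be a phone call within 7(+3) days". Section 17.2.1 follows AEs that are already recorded, and the 30-day notice in Section 17.1.1 concerns pregnancy only.

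**Sequence.** Section 10.2: "Subjects will be dosed as per a fixed sequence at Visits 2 and 3". Section 10.3.2: "As this is a fixed sequence clinical trial, every attempt will be made to maintain the masking". Section 11.3: "At Visit 2 the subjects will be randomized to receive one of the 2 treatment sequences".

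**A procedure at one dosing visit only.** Section 11.3: "Dilated funduscopy will be performed post-DEC after SVA and SLE at Visit 3". Visit 2 has no fundoscopy.

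**The concern.** The objective is to compare the safety and tolerability of two products, and the AE query is one of three safety endpoints. Section 14.1 pre-specifies no inferential analysis, so the descriptive AE table is the AE comparison that readers will have.

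That table sets a product with a return-visit query about a week after dosing beside a product whose last scheduled query is on the dosing day. A cold or headache in the week after Visit 2 is sought and recorded. The same event in the week after Visit 3 enters the data only if the subject volunteers it. If product and visit coincide, two equally tolerated products can look different.

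**Working it through.** **1. Follow-up after each product.** Visit 2 is Day 1 to 3 and Visit 3 is Day 8 to 10. The day windows alone allow gaps from 8 - 3 = 5 to 10 - 1 = 9 days. The stated minimum of 7 days between visits leaves 7 to 9 days, and the nominal gap 8 - 1 = 7 agrees with that minimum. After the Visit 3 product, scheduled observation is about 5 + 45 = 50 minutes plus the post-chamber examinations, whose length is not stated.

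**2. Model for two identical products.** n = 50 (Section 9.1). The documents give no AE rates, so these inputs are assumptions:
- b, weekly background AE risk: 2%, 5% or 10%
- a, acute dosing-day AE risk on each product: 10%, 20% or 40%
- h, hours on site after dosing: 2
- one fixed sequence for everyone, with washout-onset AEs carried to the preceding product

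For a 7-day gap, b1 = b and b2 = 1 - (1 - b)^(2/168). The probability of at least one AE is p1 = 1 - (1 - a)(1 - b1) for the first product and p2 = 1 - (1 - a)(1 - b2) for the second. Expected excess on the first product = 50 × (1 - a) × (b1 - b2).

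Example: with b = 5%, b2 = 0.0006. With a = 10%, p1 = 0.145 and p2 = 0.1005, so the excess is 50 × 0.90 × 0.0494 = 2.22 subjects.

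| b | Excess of 50 (a = 10, 20, 40%) | First product ahead | Second product ahead |
|---|---|---|---|
| 2% | 0.89, 0.79, 0.59 | 0.549, 0.529, 0.508 | 0.327, 0.375, 0.412 |
| 5% | 2.22, 1.98, 1.48 | 0.701, 0.640, 0.579 | 0.201, 0.274, 0.343 |
| 10% | 4.44, 3.95, 2.96 | 0.872, 0.792, 0.691 | 0.077, 0.147, 0.242 |

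The last two columns are exact binomial probabilities that treat the two visits as independent. With equal windows each product leads in 43-46% of trials, and the remainder are ties. If the same subjects react acutely to both products, the excess is unchanged, but at b = 5% the first product leads more often (78-89%). The excess is therefore the steadier measure.

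**3. Sensitivity.** With a 9-day gap and b = 5%, the excess is 2.84, 2.53 and 1.90. Varying h from 1 to 4 hours moves the first-ahead probability by at most 0.003. If 10-25% of background AEs are judged related (assumed), the excess in related AEs at b = 5% is 0.1-0.6 of 50. An unpaired Fisher test at b = 5% would give p < 0.05 in only 4-5% of trials.

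**4. Two sequences of 25.** Each product is given first to half the subjects, so the expected excess is 0.

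**5. Would a window ending at release be equal?** No. Visit 3 includes dilated fundoscopy before release and Visit 2 does not. If fundoscopy led to AEs in a share f of subjects (assumed 1-5%), the second product would gain about 50 × (1 - a) × f. That is 50 × 0.60 × 0.01 = 0.3 at the low end and 50 × 0.90 × 0.05 = 2.25 at the high end. The high end is as large as the imbalance at a 5% background. Section 12.2.7 also lets staff advise subjects with symptoms to stay longer, so release time can depend on the outcome.

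**The case against.** Four points can be made for the plan.

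- **A same-day focus suits the trial.** It is exploratory, gives one drop per eye per treatment visit, and sets its objective in the chamber. Section 6.4 describes the most common AE as mild, transient instillation discomfort. This stands, and it supports a same-day comparative table, which Section 14.2 does not specify.
- **The text is not silent on attribution.** Data follow the treatment actually received, and before Visit 3 only one study product has been received. This stands in part. It makes carrying washout AEs to the first product the natural reading, and that reading is what creates the imbalance. It is still not a stated rule.
- **A reader can separate the events.** Onset and relationship are tabulated, and Section 17.2.1 keeps dry eye exacerbations out of the AE data. This stands and lowers the weight.
- **The sequence is the larger issue.** With balanced sequences the imbalance cancels. With one fixed sequence, product coincides with visit for every endpoint, whatever the AE window. This also stands. Equal follow-up removes one avoidable distortion and does not repair the design.

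The size rests wholly on assumed rates, so it should be read as a range.

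**Conclusion.** The point holds conditionally. The documents establish that Section 14.2 has no common window, and that follow-up to a scheduled query is 7 to 9 days after the Visit 2 product but ends on the dosing day for completers after Visit 3. The tilt toward more AEs on the first product needs two further conditions: one fixed sequence (Sections 10.2 and 10.3.2) and attribution of washout AEs to the preceding product. Given both, the excess is about 0.6-4.4 subjects of 50 for a 7-day gap under the assumed rates. Without the first it is 0 on average. The weight is minor to moderate. The harm is to the reading of a descriptive table and not to a planned test. Follow-up length does not affect SVA, SLE or the symptom scores.

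Two stronger readings are tempting:
- A reader might infer that the AE comparison is biased whatever the sequence. Section 11.3 describes randomization to one of two sequences, and if these are balanced the imbalance cancels.
- A reader might infer that the plan misses delayed reactions to the second product. No passage reports such reactions, and AEs that subjects volunteer are still recorded.

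**What to change.** In Section 14.2, base the between-product AE table on onset within one window that is identical at both treatment visits: from instillation to completion of the post-chamber SVA and SLE, before any dilated fundoscopy. A fixed number of minutes after instillation would also serve if it ends before fundoscopy. The window should not run to release from the site.

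List all later-onset AEs separately, by visit and last product received. This includes AEs in the washout and AEs after the Visit 3 fundoscopy.

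Reconcile Sections 10.2 and 10.3.2 with Section 11.3 on the sequence. If a single fixed sequence is confirmed, state that the common window evens out follow-up but leaves product confounded with visit.

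**Cost.** This is analysis wording that can be set before database lock. AE onset date and time are already collected under Section 17.2.1. The site must be able to supply the time that closes the window, either the end of SVA and SLE or the instillation time if fixed minutes are used. The downside is that later-onset AEs leave the comparative table and appear only in the listing.

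Extending the Section 11.4 call to completers is optional and not needed for this fix. It would add about 50 calls, its present wording sets no minimum interval, and a call is not the same method as the in-person query at Visit 3.

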12. STUDY ASSESSMENTS AND PROCEDURES

12.1 Efficacy Assessments

12.1.1 Ocular Discomfort Score and Ocular Itching Score

Ocular discomfort score and ocular itching score will be measured within 15 minutes before chamber entry and over 45 minutes (every 5 minutes) in the DEC. The ocular discomfort score is a participant-reported symptom index (0 to 10 scale; 0 represents no discomfort, 10 represents maximum discomfort). Ocular itching score is a participant-reported symptom index (0 to 10 scale; 0 represents no itching, 10 represents maximum itching). The assessments of ophthalmic signs and symptoms will be self-administered by subjects using an electronic P [REDACTED].

12.2 Safety Assessments

For details regarding the timing of procedures, refer to [Table 5.1-1](#).

12.2.1 Snellen Visual Acuity (SVA)

SVA is a widely used metric for assessing the visual function that is sensitive to ophthalmic, retinal, and brain diseases. SVA chart contains lines, and each line contains five Sloan letters; the lines are all of the identical complexity, and the letter sizes increase geometrically from line to line. Each line on the chart has a similar assignment, with the font size being the only difference. Right and left eyes are tested using charts with distinct letter sequences. SVA will be measured at Visits 1, 2, and 3 as per the site's Standard Operating Procedure (SOP).

12.2.2 Slit-lamp Exam (SLE)

The slit-lamp will be placed in front of the subject's eyes and a narrow beam of bright light from the slit-lamp is directed into the eye. SLE observations will be graded as "normal" or "abnormal." Abnormal findings will be categorized as clinically significant or not. The cornea, conjunctiva, anterior chamber, lens, and eyelid will be examined. Slit-lamp Exam will be conducted at Visits 1, 2, and 3 as per the site's Standard Operating Procedure.

12.2.3 Intraocular Pressure (IOP)

The fluid pressure inside the eye is commonly known as IOP. IOP will be measured using non-contact tonometry at Visits 1 as per the site's Standard Operating Procedure.

12.2.4 Dilated Fundoscopy

Examining the fundus is an effective strategy to acquire a sense of the subject total vasculature. The investigator or qualified staff will perform a dilated fundoscopy to evaluate clinically significant fundus abnormalities and vitreous pathology. Dilated fundoscopy will be performed at Visit 1 and 3 as per the site's Standard Operating Procedure.

Safety measurements may be obtained at the discretion of the Investigator in addition to the safety assessments described in this section.

12.2.5 COVID-19 Test (SARS-CoV-2)

At Visits 1, 2, and 3, a nasal swab will be collected at the clinical site for Severe Acute Respiratory Syndrome Coronavirus 2 (SARS-CoV-2). Subjects with a positive test result will be excluded/withdrawn from the study.

12.2.6 Demographics and Medical/Medication and Ocular History

The demographic data and a complete medical/medication and ocular history will be recorded at the Screening Visit. The following demographic information will be recorded: date of birth, gender, race, ethnicity, height, and weight.

12.2.7 Adverse Event Query/Concomitant Medication Query

The staff will record all adverse events observed, queried, or spontaneously volunteered by the subjects. An adverse event query will be performed as scheduled as per Investigator's direction throughout the post-dose confinement period, prior to being released from confinement, and at each return visit for the study (if applicable). Subjects will be asked non-leading questions such

as “How do you feel now?”, “How have you felt since last asked?” or “Have you taken any medication since last asked?” If the presence of any symptom(s), adverse event(s), and/or concomitant medication is recorded, the clinical staff may advise the subjects to remain at the clinic site for safety reasons until the Investigator decides it is safe for the subjects to leave. If the subject decides to leave despite the Investigator's advice, he/she will be asked to sign a waiver.

13. ANALYSES AND REPORTS

13.1 Final Integrated Report

A final integrated report will be issued to the Sponsor (PI) by Clianza Research, which will be reviewed and released by Clianza Quality Assurance (QA). It will contain a narrative description of the clinical and statistical procedures used during the conduct of the study. Appropriate tables and graphs will be created to summarize the data.

The regulatory agency for submission will be Health Canada. The final integrated report may also be included in submissions to other international regulatory agencies.

14. STATISTICAL CONSIDERATIONS

14.1 Statistical Analyses

Due to the exploratory nature of the study, statistical analysis will be performed as required.

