5.1 Endpoints

5.1.1 Exploratory Endpoints

- Change in ocular discomfort score (0-10) from baseline over 45 minutes in the dry eye chamber
- Change in ocular itching score (0-10) from baseline over 45 minutes in the dry eye chamber

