9. SUBJECT SELECTION

9.1 Number of Subjects

The total sample size will be 50 subjects. Sufficient numbers of volunteers will be screened to enroll 50 subjects.

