10.3 Masking and Unmasking

10.3.1 Masking

This is a double-masked clinical trial. The Sponsor (PI), Investigators, qualified site personnel (except delegated unmasked pharmacy staff), and subjects will be masked to the investigational product administered until database lock. Only the delegated unmasked pharmacy staff and Scientific Affairs staff involved with preparing the assignment of Treatment A and B to the fixed sequence will have access to the treatment under evaluation.

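### The plan does not fix the summary, baseline or within-subject method for the two symptom endpoints before masking ends, and its baseline windows admit a score taken after the drop

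*Combined protocol and SAP*

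**What the plan says.** Section 14.1 states: "Due to the exploratory nature of the study, statistical analysis will be performed as required". The Study Summary repeats it. Section 14.2 covers safety only and defines only a safety population. Section 13.1 promises suitable tables and graphs. No separate analysis plan is mentioned.

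Section 5.1.1 gives the endpoints as "Change in ocular discomfort score (0-10) from baseline over 45 minutes in the dry eye chamber" and "Change in ocular itching score (0-10) from baseline over 45 minutes in the dry eye chamber". Neither is ranked above the other, and baseline is not defined for either.

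The pre-chamber score at Visits 2 and 3 is timed in two ways:

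- **From chamber entry.** Section 12.1.1 says the scores "will be measured within 15 minutes before chamber entry and over 45 minutes (every 5 minutes) in the DEC". Footnote 2 of Table 5.1-1 uses the same anchor for all visits.
- **From dosing.** Section 11.3 asks for scores "within 15 minutes prior to study treatment administration and approximately every 5 minutes while in the chamber". The Study Summary puts the first score about 15 minutes before the dose.

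The drop is given about 5 minutes before entry (Sections 8.1, 10.1 and 11.3). Table 5.1-1 also labels the Visit 1 column, where saline is given, as baseline as well as screening.

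Under Section 10.3.1 the sponsor, investigators, site staff (other than unmasked pharmacy staff) and subjects "will be masked to the investigational product administered until database lock". Section 9.1 says "The total sample size will be 50 subjects" and gives no basis for the number. Section 13.1 adds: "The final integrated report may also be included in submissions to other international regulatory agencies".

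**The concern.** A change from baseline over 45 minutes could be a mean, an area under the curve, a peak, an end value or any of nine single readings, on either of two scales. It could be taken from the same-visit score or from Visit 1. It could be analysed with or without the pairing that the crossover provides. Every one of these choices is consistent with Section 14.1, and none has to be made while the products are still masked. A nominally significant difference could therefore be one selected from many, and a reader of the report could not tell.

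The baseline timing is a separate measurement fault. Section 6.4 names mild, transient instillation site discomfort as the adverse event most often reported with reproxalap. If the baseline score can follow the drop, part of that discomfort enters the baseline and is subtracted from the change score, although the trial's objective is comparative tolerability.

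**Working it through.** **1. The plan's own figure.** The 50 subjects cannot be reproduced, because no alpha, power, SD or effect size is stated. For context, assuming two-sided 5% and 80% power, 50 pairs detect (1.960 + 0.842)/√50 = 0.396 SD of the within-subject difference.

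**2. Baseline windows on one clock** (minutes relative to chamber entry, drop at about −5):

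| Source | Time of baseline score |
|---|---|
| Study Summary | about −5 − 15 = −20 |
| Section 11.3 | −20 to −5 |
| Table 5.1-1 footnote 2, Section 12.1.1 | −15 to 0 |

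The Study Summary time lies outside the entry-based window. Section 11.3 and the entry-based window agree only from −15 to −5. From −5 to 0 a score follows the drop yet complies with Table 5.1-1 and Section 12.1.1. That is 5/15, or one third, of the entry-based window.

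Let s be the mean rise in score caused by the drop at the time of the baseline reading, and f the share of baseline readings taken after the drop, with subscripts R (reproxalap) and X (Xiidra). The reproxalap minus Xiidra difference in change from the same-visit score then shifts by −(f_R·s_R − f_X·s_X). It is unaffected if every reading precedes the drop. Otherwise the shift can hide or create a difference. The documents give no values for f or s.

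**3. The Visit 1 baseline.** In a within-subject product difference the Visit 1 score cancels: (Y_R − B1) − (Y_X − B1) = Y_R − Y_X. Choosing Visit 1 therefore means comparing unadjusted chamber scores, which is a different analysis from same-visit change.

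**4. Effect of selection.** Readings at 5 to 45 minutes number nine, so two scales give 2 × 9 = 18 contrasts. If these were independent, the chance of at least one p<0.05 would be 1 − 0.95^18 = 60%. Simulated paired t-tests (50 pairs, no true difference, two-sided 5%, 20,000 replicates, assumed correlations between contrasts) give:

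| Within scale | Across scales | At least one p<0.05 |
|---|---|---|
| 0.5 | 0.3 | about 45% |
| 0.9 | 0.3 | about 23% |
| 0.9 | 0.9 | about 15% to 16% |

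A second simulation (5,000 runs per setting) let adjacent readings correlate at 0.70 to 0.95 and the two scales at 0.3 to 0.8:

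| Choice left open | At least one p<0.05 |
|---|---|
| One fixed analysis | about 5% |
| Two endpoints, one summary, one baseline | 7.4% to 10.8% |
| Two endpoints, 12 summaries (three time averages and nine single readings) | 17.2% to 45.7% |
| The same, with same-visit or Visit 1 baseline | 30.6% to 65.9% |

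In the widest search the largest |t| passed 2.95 to 3.34 (p about 0.005 to 0.0016) in only 5% of null trials. With 50 pairs that is 2.95/√50 = 0.42 to 3.34/√50 = 0.47 SD.

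**5. Within-subject method.** Ignoring the pairing multiplies the standard error by 1/√(1 − r). For assumed between-visit correlations r of 0.3, 0.5 and 0.7 the factor is 1.20, 1.41 and 1.83.

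A mixed model on all nine readings with a random subject effect alone errs the other way, because it treats readings within a visit as nearly independent. Under no product effect, with 50 subjects, two balanced orders and subject-by-visit variance assumed at 5% to 50% of the total, such a model rejected in 18% to 53% of trials. A repeat over the same variance range gave about 15% to 57%. A test on visit means rejected in 4% to 5%.

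**6. Treatment order.** Sections 10.2 and 10.3.2 describe a fixed sequence, while Section 11.3 randomizes subjects to one of two. With one order for everyone, the product and visit columns are identical: intercept, product and visit have rank 2, not 3. No model can then separate product from visit.

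**The case against.** The strongest reply is that the endpoints are labelled exploratory throughout and that no hypothesis, alpha or confirmatory claim is made. Section 13.1 says only that the report may enter other submissions. This stands as a limit on the harm: formal error control is not owed. It does not remove the need to say what the endpoint is, since the objective is a comparison with Xiidra and Section 13.1 names Health Canada as the agency for submission.

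Three stronger readings are tempting, and the documents do not support them.

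- A reader might infer that any product difference could be an artefact of selection. Step 4 shows otherwise: a difference well beyond p = 0.002, or one consistent over time and on both scales, is not explained by selection alone.
- A reader might infer that the analysis will be chosen after unmasking. Section 10.3.1 says when masking ends, not when the analysis is chosen. The documents allow a late choice by silence only.
- A reader might infer that the conflicting windows give the analyst two baselines to pick from. Table 5.1-2 schedules one time-0 score per visit, so they make that score inconsistently timed. The choice open to the analyst is same-visit score or Visit 1, and the latter rests only on a column label.

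It is also fair to say that a 45-minute mean dilutes an early instillation effect, and that nothing in the documents favours discomfort over itching. Both choices belong to the sponsor.

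**Conclusion.** The point holds in this form: the summary, baseline and within-subject method for both symptom endpoints are not fixed, nothing requires them to be fixed before lock, and two of the stated timing rules permit a baseline score after the drop. None of this is a redaction gap, since Section 14.1 is a complete sentence.

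Nominal differences near p = 0.05 would be unreliable. Over the 18 contrasts the false-positive chance is about 23% to 45% (correlations 0.9 to 0.5 within scale, 0.3 across), about 16% at 0.9 for both and 60% if independent, against about 5% for one fixed analysis. These figures rest on assumed correlations and an assumed two-sided 5% test. The size of the post-drop baseline bias cannot be computed from the documents. Its existence follows from the windows whenever readings fall after a drop that changes the score, unless the shifts for the two products happen to cancel.

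**What to change.** 1. Reconcile the Study Summary, Table 5.1-1, Section 11.3 and Section 12.1.1 so that baseline for both endpoints is the same-visit score taken before the drop. State that the Visit 1 label does not define the endpoint baseline.
2. Reconcile Sections 10.2 and 10.3.2 with Section 11.3 on treatment order. If there are two orders, include a visit (period) effect. If there is one, leave it out and say in the report that product and visit cannot be separated.
3. Before database lock, replace Section 14.1 with one summary per endpoint, for example the mean change over the nine readings at 5 to 45 minutes. Show the time course descriptively so that an early instillation effect stays visible. State which endpoint leads, the analysis set and the handling of missing scores.
4. Report the paired reproxalap minus Xiidra difference with a 95% confidence interval. Use visit-level summaries, or a mixed model with subject and subject-by-visit effects (or an equivalent within-visit covariance). A random subject effect alone is not enough.

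The cost is about half a page of wording and no new data. The sponsor gives up free choice of summary and time point after lock. With a single order, this wording does not remove the confounding of product with visit; it only discloses it.
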